5.5. Packaging and Labeling

The contents of the label will be in accordance with all applicable regulatory requirements.

5.6. Preparation/Handling/Storage/Accountability

No special preparation of study treatment is required.

- Only subjects enrolled in the study may receive study treatment and only authorized site staff may supply or administer study treatment. All study treatments must be stored in a secure environmentally controlled and monitored (manual or automated) area in accordance with the labelled storage conditions with access limited to the investigator and authorized site staff.
- The investigator, institution, or the head of the medical institution (where applicable) is responsible for study treatment accountability, reconciliation, and record maintenance (i.e. receipt, reconciliation and final disposition records).
- Further guidance and information for final disposition of unused study treatment are provided in the Study reference Manual (SRM).
- Under normal conditions of handling and administration, study treatment is not expected to pose significant safety risks to site staff
- A Material Safety Data Sheet (MSDS)/equivalent document describing occupational hazards and recommended handling precautions either will be provided to the investigator, where this is required by local laws, or is available upon request from GSK.

5.7. Compliance with Study Treatment Administration

When the individual dose for a subject is prepared from a bulk supply, the preparation of the dose will be confirmed by a second member of the study site staff.

When subjects are dosed at the site, they will receive study treatment directly from the investigator or designee, under medical supervision. The date and time of each dose administered in the clinic will be recorded in the source documents. The dose of study treatment and study subject identification will be confirmed at the time of dosing by a member of the study site staff other than the person administering the study treatment. Study site personnel will examine each subject's mouth to ensure that the study treatment was ingested.

When subjects self-administer study treatment(s) at home, compliance with study drug will be assessed through querying the subject during the site visits and documented in the source documents and CRF. A record of the number of study drug tablets dispensed to and taken by each subject must be maintained and reconciled with study treatment and compliance records. Treatment start and stop dates, including dates for treatment delays and/or dose reductions will also be recorded in the CRF.

5.8. Treatment of Study Treatment Overdose

GSK does not recommend specific treatment for an overdose. The investigator or physician in charge of the subject at the time will use clinical judgment to treat any overdose.

5.9. Treatment after the End of the Study

Subjects will not receive any additional treatment from GSK after completion of the study because only healthy subjects or healthy obese subjects are eligible for study participation.

5.10. Lifestyle and/or Dietary Restrictions

5.10.1. Meals and Dietary Restrictions

Subjects should refrain from consumption of red wine, Seville oranges, grapefruit or grapefruit juice and/or pummelos, exotic citrus fruits, grapefruit hybrids or fruit juices from 7 days prior to the first dose of study medication until after the final dose.

Subjects in Part 3, evening dosing, should refrain from any meals after the evening dose until breakfast the next morning.

5.10.2. Caffeine, Alcohol, and Tobacco

- For Part 1 and Part 2, subjects will abstain from ingesting caffeine- or xanthine-containing products (e.g., coffee, tea, cola drinks and chocolate) for 24 hours prior to the start of dosing until collection of the final pharmacokinetic and or pharmacodynamic sample during each cohort.
- For Part 3, during each inpatient visit, subjects will abstain from ingesting caffeine- or xanthine-containing products (e.g., coffee, tea, cola drinks and chocolate) for 24 hours prior to the start of dosing until collection of the final pharmacokinetic and or pharmacodynamic sample during the inpatient stay.
- During each dosing session, subjects will abstain from alcohol for 24 hours prior to the start of dosing until collection of the final pharmacokinetic and or pharmacodynamic sample during each session.
- For Part 1 and Part 2, use of tobacco products is not allowed from inpatient check-in and the start of dosing until after the final follow-up visit.
- For Part 3 inpatient sessions, use of tobacco products is not allowed from inpatient check-in until after discharge from the unit.
- For Part 3, outpatient Subjects who use tobacco products will be instructed that use of nicotine-containing products (including nicotine patches) will not be permitted while they are in the Clinical Unit.

5.10.3. Activity

Subjects will abstain from strenuous exercise for 1 hour prior to each blood collection for clinical laboratory tests. Subjects may participate in light recreational activities during studies (e.g., watch television, read).

5.11. Concomitant Medications and Non-Drug Therapies

Based on the *in vitro* data generated to date, it is unlikely for GSK3008356 to affect the pharmacokinetics of co-administered CYP, OATP1B1/1B3, P-gp or BCRP substrates. Please refer to the IB [GlaxoSmithKline Document Number [2015N255332_00](#)] for details.

5.11.1. Permitted Medications and Non-Drug Therapies

Paracetamol, at doses of ≤ 1 grams/day is permitted for use any time during the study. Other concomitant medication may be considered on a case by case basis by the investigator in consultation with the Medical Monitor if required.

5.11.2. Prohibited Medications and Non-Drug Therapies

Subjects must abstain from taking prescription or non-prescription drugs (including vitamins and dietary or herbal supplements), within 7 days (or 14 days if the drug is a potential enzyme inducer) or 5 half-lives (whichever is longer) prior to the first dose of study medication until completion of the follow-up visit, unless in the opinion of the Investigator and sponsor the medication will not interfere with the study.

6. STUDY ASSESSMENTS AND PROCEDURES

Protocol waivers or exemptions are not allowed with the exception of immediate safety concerns. Therefore, adherence to the study design requirements, including those specified in the Time and Events Table, are essential and required for study conduct.

This section lists the procedures and parameters of each planned study assessment. The exact timing of each assessment is listed in the Time and Events Table Section [6.1](#)

The following points must be noted:

- If assessments are scheduled for the same nominal time, THEN the assessments should occur in the following order:
 1. 12-lead ECG
 2. vital signs
 3. blood draws
 4. skin biopsy.

Note: The timing of the assessments should allow the blood draw to occur at the exact nominal time.

[figure not shown]
- The timing and number of planned study assessments, including safety, pharmacokinetic, pharmacodynamic/biomarker or others assessments may be altered during the course of the study based on newly available data (e.g., to obtain data closer to the time of peak plasma concentrations) to ensure appropriate monitoring.

- The nominal dosing time for evening dose cohorts (20:00 local) in the respective Time and Events Tables is for illustrative purposes only. The nominal evening dose time selected for use will be documented for each evening dose cohort. The actual dose time will be recorded as well.
- The change in timing or addition of time points for any planned study assessments must be documented in a Note to File which is approved by the relevant GSK study team member and then archived in the study sponsor and site study files, but this will not constitute a protocol amendment.
- The HREC and investigators will be informed of any safety issues that require alteration of the safety monitoring scheme or amendment of the Informed Consent Form.
- No more than 650 mL of blood will be collected over the duration of the study, including any extra assessments that may be required.

6.1. Time and Events Tables

Please refer to [Figure 3](#) below to understand the how the multiple Time and Events Tables relate to the study Parts.

Figure 3 Study Part and Related Time and Events Tables

6.1.1. Part 1 – Single Dose

	Screening (within 28d)	Day -2, Day -1 ⁹	Day 1													Day 2	Day 3	Day 4	Follow Up (Day 6-8)
			Pre-dose	0h	0.25h	0.5h	1h	1.5h	2h	4h	6h	8h	12h	18h	24h	36h	48h	72h	
Informed Consent	X																		
Medical/medication/drug/alcohol history	X	X																	X
Complete Physical Exam, Weight	X	X ¹																X ¹	X
HIV, Hep B, Hep C	X																		
Pregnancy Test ²	X	X																	X
Estradiol/FSH ³	X																		
Urine Drug, Cotinine & Alcohol Screen ⁴	X	X																	
Fat Meal ⁵		X							X										
Triglyceride Assessment ⁵		←→					X	←-----→											
Study Drug Dose ¹⁰				X ¹⁰															
Vital Signs (BP, HR, pulse, Temp) ⁶	X	X	X				X			X			X		X		X	X	X
12-Lead ECG	X		X				X			X			X		X			X	
Telemetry			←-----→																
Hematology, Chemistry	X	X										X			X		X	X	X
UA	X	X												X			X	X	
Exploratory PD Labs	X		X											X			X	X	
Plasma PK and Metabolite Sampling ^{5,7}			X		X	X	X	X	X	X	X	X	X	X	X	X	X	X	
Urine PK and Metabolite Sampling ⁷			←→	←-----→										←→					
Adverse Event Review			←-----→																
BSFS ⁸			←-----→																
Concomitant Medication Review			←-----→																
Outpatient Visits	X																		X
Inpatient Check-in		X																	
Inpatient Check-out																		X	

1. Brief physical exam, weight.
2. Serum hCG at screening and follow up, urine hCG pre-dose on Day -1 – all females.
3. If indicated.
4. An alcohol breath test is acceptable.
5. Detailed Fat Meal and Triglyceride Assessment relative to Dose and Plasma PK Sampling can be found in Section 6.1.1.1.
6. Temperature Screening and Day -1 only.
7. Plasma analysis for circulating metabolite profile; Urine analysis to aid structural identification. Urine samples for parent and metabolite structure will be collected pre-dose and over the post-dose intervals 0-12 hours and 12-24 hours. Plasma and urine samples for metabolites will be analyzed from only the highest dose cohort.
8. The number of BSFS stool types will be collected in real time for each 24h period (Section 11.5).
9. Based on logistics, check-in and all Day -1 assessments may occur on Day -2 with the exception of the Fat Meal and TG Assessment, both of which must be done on Day -1.
10. For cohorts where multiple doses are to be administered either q1h, q4h or q16h, Time 0 is the first dose and subsequent doses are per regimen (q1h, q4h or q16) and the subsequent doses are not noted on the T&E Table. For the single evening cohort, the dose will be at hour 16 and not noted on the T&E Table.

6.1.1.1. Part 1, Single Dose, Fat Meal Challenge and Triglyceride Assessment Relative to Dose and PK Sampling

	Day -1, Day 1															
	Pre-dose	0h	0.25h	0.5h	1h	1.5h	2h	3h	4h	5h	6h	7h	8h	9h	12h	18h
Study Drug Dose ^{1,3}		X ³														
Fat Meal							X									
Triglyceride Assessment					X		X	X	X	X	X	X	X	X	X	
Plasma Pharmacokinetic Sampling ^{1,2}	X		X	X	X	X	X		X		X		X		X	X

1. Day 1 only
2. PK Samples included in table to provide relative time to dosing, fat meal and triglyceride assessment.
The full PK time points are found in Section 6.1.1
3. For cohorts where multiple doses are to be administered either q1h, q4h or q16h, Time 0 is the first dose and subsequent doses are per regimen (q1h, q4h or q16) and the subsequent doses are not noted on the T&E Table. For the single evening cohort, the dose will be at hour 16 and not noted on the T&E Table

6.1.2. Part 2 – Repeat Dose, Morning Dose Administration, Screening, Day -1, Day 1

	Screening (within 28d)	Day -2, Day -1 ⁹	Day 1													
			Pre-dose	0h	0.25h	0.5h	1h	1.5h	2h	4h	6h	8h	12h	18h	24h	
Informed Consent	X															
Medical/medication/drug/alcohol history	X	X														
Complete Physical Exam, Weight	X	X ¹														
HIV, Hep B, Hep C	X															
Pregnancy Test ²	X	X														
Estradiol/FSH ³	X															
Urine Drug, Cotinine & Alcohol Screen ⁴	X	X														
Fat Meal ⁵		X							X							
Triglyceride Assessment ⁵		←→					X	←=====→								
Study Drug Dose ¹⁰				X ¹⁰												
Vital Signs (BP, HR, pulse, Temp) ⁶	X	X	X				X				X			X		X
12-Lead ECG	X		X				X				X			X		X
Telemetry			←=====→													
Hematology, Chemistry	X	X										X				X
UA	X	X														X
Exploratory PD Labs	X		X													X
Plasma PK and Metabolite Sampling ^{5,7}			X		X	X	X	X	X	X	X	X	X	X	X	X
Adverse Event Review			←=====→													
BSFS ⁸			←=====→													
Concomitant Medication Review			←=====→													
Outpatient Visits	X															
Inpatient Check-in		X														

1. Brief physical exam, weight.
2. Serum hCG at screening and follow up, urine hCG pre-dose on Day -1 – all females.
3. If indicated.
4. An alcohol breath test is acceptable.
5. Detailed Fat Meal and Triglyceride Assessment relative to Dose and Plasma PK Sampling can be found in Section [6.1.8.1](#).
6. Temperature Screening and Day -1 only.
7. Plasma analysis for circulating metabolite profile; Plasma samples for metabolites will be analyzed from only the highest dose cohort.
8. The number of BSFS stool types will be collected in real time for each 24h period (Section [11.5](#)).
9. Based on logistics, check-in and all Day -1 assessments may occur on Day -2 with the exception of the Fat Meal and TG Assessment, both of which must be done on Day -1.
10. For cohorts where multiple doses are to be administered either q1h or q16h, Time 0 is the first dose and subsequent doses are per regimen (q1h or q16) and the subsequent doses are not noted on the T&E Table.

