While the adjusted doses did allow observation of a PD response in Cohort 5, the overall single dose data were limited and could not adequately inform a PK/PD model or support informed progression into Part 2 of the study. It was determined to further explore the PK/PD through additional Part 1 cohorts. The purpose of the additional cohorts is to explore dose administration in a manner that should provide a more acceptable PK profile than that observed to date. This includes divided doses to achieve time above the target exposure with varying levels of C_{max} and doses directly related to regimens that may be used in Part 2 of the study. There will be no changes to the current challenge meal or assessments.

3.1.2. Revised Dosing Regimens for Part 2

Based on preliminary PK data from Part 1, the doses and regimens are now better clarified for Part 2. Part 2 Cohorts 1, 2 and 3 will be administered in the AM as divided doses to achieve a daily time above the target exposure with varying levels of C_{max}. Specifically, Cohort 1 will have a regimen of 2 doses separated by 16 hours similar to Part 1 Cohort 8. The purpose is to explore a BID PK profile. Cohorts 2 and 3 will have a regimen of nine hourly doses similar to Part 1 Cohorts 10 and 11. The purpose is to explore PK profiles that approximate a sustained release formulation to guide further dosage development. There will be no changes to the current challenge meal or assessments except for the addition of a skin biopsy outlined in Section 6.4.5.

The regimens are as follows:

Part 2, Cohort 1 would evaluate 10 mg administered twice at time 0h and 16h for a total dose of 20 mg.

Part 2, Cohort 2 would evaluate 27 mg daily administered as 9 doses of 3 mg hourly from time 0 to time 8h daily for 14 days.

Part 2, Cohort 3 would evaluate either 9 mg daily administered as 9 doses of 1 mg hourly from time 0 to time 8h or 45 mg daily as 9 doses of 5 mg hourly from time 0 to time 8h.

Neither the predicted human C_{max}, nor the predicted daily human AUC of evaluated doses is expected to exceed the dog NOAEL exposure of C_{max} (7.73 µg/mL) and AUC(0-t) (111 µg.h/mL).

However, data from a 13-week oral toxicity study in dogs indicate that the NOAEL for dosing duration >28 days will likely be lower than the current NOAEL. While these dog data do not impact the risk for this protocol as they do not change the NOAEL (Section 3.5.1), these data will impact the future viability of certain dose regimens.

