The regimens selected for Part 2 as outlined above are regimens have future development viability based on human exposure below the oral 13-week repeat dose dog testicular observation NOAEL exposure of C_{max} (0.642 µg/mL) and AUC(0-t) (5.49 µg.h/mL).

The highest dose regimen planned for Part 3 (45 mg daily as 9 doses of 5 mg hourly from time 0 to time 8h) is expected to result in the highest Part 2 C_{max} (0.203 µg/mL) and AUC (1.261 µg.h/mL) exposure, based on Part 1 data.

These predicted exposures are still 3.2-fold and 4.4-fold below the oral 13-week repeat dose dog testicular observation NOAEL C_{max} and AUC exposure, respectively. The predicted exposures are 38.1-fold and 88.1-fold below the current NOAEL C_{max} and AUC exposure, respectively.

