### 11.3. Appendix 3: Assessment Windows

#### 11.3.1. Definitions of PK Assessment Windows

Analysis Set / Domain	Target / nominal time	Target Window		Analysis Timepoint
		Beginning Timepoint	Ending Timepoint	
PK Concentration (analyte is GSK3008356)	Pre-Dose	within 30 mins of dosing	dosing time	0 Hours
	0.25 hour	00:13	00:17	Actual draw time
	0.5 hour	00:27	00:33	Actual draw time
	1 hour	00:57	01:03	Actual draw time
	1.5 hours	01:27	01:33	Actual draw time
	All Subsequent draws between 2 hours – 24 hours*	Target – 00:10	Target + 00:10	Actual draw time
	All Subsequent draws between 36 hours – 72 hours*	Target – 00:30	Target + 00:30	Actual draw time

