**NOTES :**

- Any actual draws outside of these time windows will be listed as deviations (not necessarily “important”), but will still be used in the concentration assay and determination of PK parameters according to the actual draw time.
- Any concentrations determined from blood draws inside or outside these windows may still be excluded from PK determinations for other reasons, such as sample handling or other protocol deviations.
- \* All Subsequent draws after 2 hour will be at hours 4, 6, 8, 12, 18, 24, 36, 48, and 72 in Part 1.
- In Part 2, All Subsequent draws after 2 hour will be at hours 4, 6, 8, 12, and 18 on Day 1; then PK Samples will be taken at Pre-Dose on Days 2, 4, 5, 6, 12, and 13 only during period Days 2-13 Morning Dose; and starting on Day 14, PK Samples will be taken at Pre-dose, hours at 0.25, 0.5, 1, 1.5, 2, 4, 6, 8, 12, 18, 24, 36, 48, and 72.

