### 11.3.3. Definitions of Vital Signs and ECG Assessment Windows

Analysis Set / Domain	Target / nominal time	Target Window		Analysis Timepoint
		Beginning Timepoint	Ending Timepoint	
Vital Signs (BP, HR, pulse, Temp.)* and 12-Lead ECG	Screening	Within 28 day	Day -1	Screening
	Checking in	Day -1	Day -1	Day -1
	Pre-Dose	Within 12 hours before dosing	dosing time	00:00
	1 Hour Post-Dose	Target – 00:15	Target + 00:15	+01:00
	4 Hours Post-Dose	Target – 00:15	Target + 00:15	+04:00
	12 Hours Post-Dose	Target – 00:15	Target + 00:15	+12:00

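### For divided doses the PK, ECG and vital-sign schedule stayed anchored to the first dose, so the peak after the last dose is unsampled under hourly and 0h/4h dosing

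*Protocol*

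**What the plan says.** Protocol 6.1.1 (footnote 10) sets the time origin for divided regimens: "Time 0 is the first dose and subsequent doses are per regimen (q1h, q4h or q16". The later doses are not placed on the table. The Part 2 morning tables (6.1.2 to 6.1.4) carry the same rule for q1h and q16h.

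The assessments were kept as they were. For the added Part 1 cohorts, Protocol 3.1.1 says: "There will be no changes to the current challenge meal or assessments". For Part 2, 3.1.2 says: "There will be no changes to the current challenge meal or assessments except for the addition of a skin biopsy".

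The SAP, written after Part 2 ended, lists the same times. Its PK window notes (11.3.1) read: "All Subsequent draws after 2 hour will be at hours 4, 6, 8, 12, 18, 24, 36, 48, and 72 in Part 1". Its ECG and vital-sign windows (11.3.3) go from 4 hours to "12 Hours Post-Dose".

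Protocol 3.1.2 describes the hourly regimen as, for example, "45 mg daily as 9 doses of 5 mg hourly from time 0 to time 8h". Per SAP 11.5.1, hourly dosing was given only in Part 1 Cohorts 10 (10 mg) and 11 (5 mg). Cohort 7 was dosed at 0h and 4h. Cohort 8 and all of Part 2 are shown as 0h/16h or BID.

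Protocol section 6 orders coincident assessments as ECG, vital signs, blood, biopsy. It does not say where a coincident dose falls in that order.

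**The concern.** The divided cohorts were added to study time above a target exposure at varying Cmax, and the hourly ones to imitate a sustained-release profile (Protocol 3.1.1, 3.1.2). With accumulation, the highest concentration follows the last dose, and that is where the schedule has its gap. The draws at 1, 2, 4, 6 and 8h share their nominal times with hourly doses. If taken first, they are troughs.

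Three uses are affected. Cmax and AUC are secondary endpoints, and SAP 8.1.3.1 summarises them for every active regimen without caveat. SAP 8.1.3.2 models AUC(0-∞) for the divided Part 1 regimens, so error in AUC enters a formal dose-proportionality analysis. ECG and vital signs are primary safety endpoints, yet no scheduled QTcF or blood pressure lies near the last-dose peak.

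**Working it through.** **1. The plan's own margins.** Protocol 3.1.2 gives Cmax 0.203 µg/mL and AUC 1.261 µg.h/mL for 5 mg hourly × 9.
- 13-week dog NOAEL: 0.642/0.203 = 3.16 and 5.49/1.261 = 4.35, matching the stated 3.2 and 4.4.
- 4-week dog NOAEL: 7.73/0.203 = 38.1 and 111/1.261 = 88.0 (stated 88.1, a rounding difference).

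**2. Last dose against the schedule.**

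| Regimen | Last dose | PK draws around it | ECG/vitals around it |
|---|---|---|---|
| Hourly × 9 | 8h | 8h, then 12h | 4h, then 12h |
| 0h/4h | 4h | 4h, then 6h | 4h, then 12h |
| 0h/16h | 16h | 12h, then 18h | 12h, then 24h |

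Blood is also drawn at 5h and 9h on Day 1, but for triglycerides only.

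**3. Model.** One compartment, linear, per unit dose:
- c(t) = ka·ke/(ka−ke) × (e^(−ke·t) − e^(−ka·t)), with ke = ln 2/half-life.
- C(t) is the sum of c(t − d) over dose times d.
- Half-life 1.5-3h is the observed range in Protocol 3.1.1. The ka of 1.4 per h is from Protocol 3.4.2; the upper value of 10 per h is an assumption.
- AUC(0-24) uses the SAP's linear-up, log-down rule at the scheduled times.

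**4. One case by hand** (hourly, half-life 1.5h, ka 10, draw just before the dose; common factor omitted). ke = 0.462.
- At 8h, eight earlier doses: 0.630 × (1 − 0.630^8)/(1 − 0.630) = 1.660.
- At 8.22h, with the ninth: 2.660 × e^(−0.462×0.22) − e^(−10×0.22) = 2.403 − 0.111 = 2.292.
- Ratio 1.660/2.292 = 0.724, so sampled Cmax is 28% low.

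**5. Range over the grid** (sampled as % of true).

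| Regimen | True peak | Coincident draws | Cmax | AUC(0-24) |
|---|---|---|---|---|
| Hourly × 9 | 8.2-8.5h | pre-dose | 72-93% | 81-94% |
| Hourly × 9 | 8.2-8.5h | 10 min post-dose | 96-99% | 95-108% |
| 0h/4h | 4.3-5.3h | pre-dose | 70-94% | 80-94% |
| 0h/16h | 16.3-17.5h | none | 96-100% | 99-111% |

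Ten minutes is the SAP limit for "All Subsequent draws between 2 hours – 24 hours".

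**6. Sensitivity to model shape.** Table 5's observed single-dose Cmax/AUC ratios run from 0.34 per h (1865.3/5488, 200 mg) to 0.61 per h (191/314, 10 mg). One- and two-exponential profiles matched to that range, with pre-dose draws, give hourly Cmax 61-83% and AUC(0-∞) 73-87% of true. The direction for pre-dose draws is stable; the size depends on the model.

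**7. Protocol 3.1.2 against Table 5, same regimen.** Cmax is 203 against 150 ng/mL (203/150 = 1.35). AUC is 1261 against 1297 ng.h/mL (1261/1297 = 0.97). The 3.1.2 pair has Cmax/AUC = 0.203/1.261 = 0.161 per h. The hourly profiles in step 5 have a true ratio of at most 0.123 per h. Also, 1.5 × the observed 30 mg AUC of 841 is 1261.5, which equals the 3.1.2 AUC to rounding, although the documents do not say it was obtained that way.

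**The case against.** The strongest reply is that the protocol already provides the remedy. Section 6 and 6.4.1 allow timing changes or added samples by Note to File. This stands as permission only: nothing requires a change, and the later SAP lists the same times with none added.

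Second, draw order is unstated, so understatement is conditional. This stands. Draws 10 minutes after the dose nearly remove the hourly Cmax error, and AUC may then be slightly low or too high.

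Third, peak safety is not wholly missed. This also stands. Adverse-event review is continuous, and telemetry runs on Day 1. Single doses up to 200 mg, with higher observed Cmax (1865 ng/mL) than Table 5 predicts for any hourly regimen (150-600 ng/mL), had an ECG and vital signs at 1h.

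Fourth, scope is small: hourly dosing reached two Part 1 cohorts, and Cmax is not modelled for divided Part 1 regimens. That limits the consequence but not the need for a caveat on the reported values.

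A reader might go further and infer that the 3.2-fold cover in Protocol 3.1.2 is overstated. The documents do not support this. They do not say how 0.203 µg/mL was obtained, it exceeds Table 5's prediction, and its ratio to AUC is more peaked than any hourly profile in step 5, which is not what trough-only sampling would produce. Even if Cmax were the lowest fraction found, 61% of true, the cover would be about 3.16 × 0.61 = 1.9-fold, so the NOAEL exposure would not be crossed.

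**Conclusion.** The schedule was not re-anchored when dosing became divided, and the last-dose peak is unsampled for hourly and 0h/4h regimens. If coincident draws precede the dose, sampled Cmax is about 7-28% low (hourly) or 6-30% low (0h/4h), and AUC about 6-20% low. This assumes linear one-compartment kinetics, half-life 1.5-3h and ka 1.4-10 per h. The direction of the AUC error is uncertain until draw order is known. Cmax for 0h/16h is adequate; what that regimen lacks is a scheduled ECG and vital signs between the 16h dose and 24h.

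Two stronger inferences fail: that peak-exposure safety went unobserved, and that the NOAEL margins are wrong. What can be said of the margins is that 3.1.2 and Table 5 give different exposures for one regimen and must be reconciled.

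**What to change.** **Data already collected (SAP).**
- Report Cmax in Cohorts 7, 10 and 11 as the highest scheduled sample, a lower bound.
- State whether coincident draws preceded or followed the dose.
- Derive peak and AUC by superposition or a PK model.
- Say how 0.203 µg/mL and 1.261 µg.h/mL were obtained, and reconcile them with Table 5's 150 ng/mL and 1297 ng.h/mL. Restate the 3.2-fold and 4.4-fold cover only if they came from this schedule.

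**Any further divided-dose cohort (footnotes in 6.1.1, 6.1.2 and 6.1.4).**
- State that coincident PK draws are taken immediately before the dose.
- Hourly: move the 0.25h and 1.5h draws to 8.5h and 10h, and take an aliquot of the 9h triglyceride draw.
- 0h/4h: move one early draw to about 4.5h and use the 5h triglyceride draw.
- Move one existing ECG and vital-sign set to about 1h after the last dose of the day.

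In the same model the hourly changes bring sampled Cmax to 92-100% of true but AUC only to 84-97%, because most of the AUC error comes from draws at dose times. The modelling step is therefore needed either way.

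The cost is a few footnotes and one SAP paragraph. Draws are moved or shared, so blood volume barely changes against the 650 mL limit. The downside is fewer points on the first-dose rise.
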